3.5 End of trial assessment

The end of trial is the date of the last visit of the last participant.

Visits: Day 30 \pm 5 and Day 90 \pm 7.

Setting: Outpatient basis.

e-CRF entries:

- Recording of concomitant medications
- Symptomatic new or recurrent VTE
- Death
- Primary cause of death
- Major bleeding
- Clinically relevant non-major bleeding
- Serious adverse events
- Rehospitalization
- Primary cause of rehospitalization

4. STUDY ORGANIZATION

4.1 Steering Committee

The Steering Committee will meet periodically to assess the progress, provide scientific input on the protocol and possible amendments as well as on the “state of the art” and any ongoing development during the study which could have consequences for the performance of the study, and address policy issues and operational aspects of the protocol and recommendations of the Data safety Monitoring Board (**DSMB**).

4.2 Investigators

Participating investigators will be responsible for enrollment of patients who meet the inclusion and none of the exclusion criteria, obtaining informed consent, and management of patients randomized to the intervention.

Participating investigators will not be allowed to manage patients randomized to usual care.

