Control group: All included patients will undergo standard clinical management of their exacerbations, as deemed appropriate by the attending physician.

Criteria for efficacy:

Primary end point

- Clinical composite endpoint of all-cause mortality or venous thromboembolism recurrence or need for COPD readmission within 90 days.

Secondary end points

- All-cause mortality within 90 days.
- Venous thromboembolic recurrence within 90 days.
- Need for COPD readmission within 90 days.
- Length of hospital stay.

Criteria for safety:

Primary end point

- Major bleeding within 90 days.

Secondary end points

- Clinically relevant non-major bleeding within 90 days.
- Serious adverse events within 90 days.

Statistical analysis: Intent-to-treat (ITT) analysis on superiority of an active strategy for the diagnosis and treatment of PE in patients with unexplained exacerbations of COPD requiring hospital admission.

Primary criteria

The primary ITT analysis on the primary end points will be carried out by a two-sided chi-square test on proportions. In addition, the 95% confidence interval on the relative risks will be presented.

Secondary efficacy criteria

The secondary ITT analysis on the secondary efficacy end points will be carried out by a two-sided chi-square test on proportions. In addition, the 95% confidence interval on the relative risks will be presented. The survival status during 90 days follow-up will be analyzed by showing Kaplan-Meier curves, and management differences will be compared by means of log-rank test.

Secondary safety analysis

Safety end points will be tabulated by management group. All (dichotomized) end points will be analyzed by chi-square test on proportions, and the 95% confidence interval on the relative risks will be presented. In addition, continuous safety monitoring will be done by the Data and Safety Monitoring Board.

Interim analysis

Interim analysis will be made by the Data Center after recruitment of 50% of the total number of patients. These analyses will be made in order to allow sample size reassessment or early stop of the trial for efficacy or futility.

TABLE OF CONTENTS	Page
ABBREVIATIONS	15
1. BACKGROUND	16
1.1 Study justification	16
1.2 Hypothesis	17
1.3 Objectives	17
2. METHODOLOGY	20
2.1 Design	20
2.2 Setting	20
2.3 Study subjects	21
2.4 Randomization	22
2.5 Study procedures	22
2.6 Criteria for termination of the trial	23
2.7 Definition of study end points	23
2.8 Surveillance and follow-up	28

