2. METHODOLOGY

2.1 Design

SLICE is an investigator-initiated, phase III, prospective, multicenter, randomized (1:1), open-label with blind end-point evaluation (**PROBE**), parallel-group trial comparing the efficacy and safety of an active search for PE (intervention group) with usual care (control group) in patients with unexplained exacerbations of COPD who require hospital admission (ClinicalTrials.gov identifier NCT02238639).

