2.5 Study procedures

All patients will receive standard clinical management (usual care) for their COPD exacerbation according to the clinician's preference and local standards.

Intervention group

Patients in the intervention group will have blood samples collected from an antecubital vein, and will undergo D-dimer testing within 12 hours after randomization. Cut-off levels for defining elevated D-dimer will be defined by the Department of Clinical Chemistry at each participating site. For patients with a negative D-dimer, a diagnosis of PE will be ruled out. For patients with a positive D-dimer, a contrast-enhanced, PE-protocol, multidetector CT will be performed. CT pulmonary angiography results will be categorized as positive for PE if an intraluminal filling defect is seen in (sub)segmental or more proximal branches, and will be considered negative if no filling defect is observed. Scans will be considered technically inadequate only if main or lobar pulmonary vessels are not visualized. Though not mandatory, the protocol suggests the use of complete lower limb compression ultrasonography (**CCUS**) to detect concomitant DVT for patients with isolated subsegmental PE.

If the diagnosis of PE is confirmed, patients will receive anticoagulant treatment according to guideline recommendations: parenteral anticoagulation (i.e.,

unfractionated heparin, low-molecular-weight heparin, or fondaparinux) overlapped and followed by vitamin K antagonists; or parenteral anticoagulation followed by dabigatran or edoxaban; or monotherapy with apixaban or rivaroxaban (19).

Control group

Patients in the control group will receive standard clinical management (usual care) for their COPD exacerbation according to the clinician's preference and local standards.

After hospital discharge, all patients (in the intervention and control arms) will be treated according to the national and international recommendations for the management of stable COPD (1, 2).

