2.7 Definition of study end points

Efficacy

The primary efficacy end point is the composite of death from any cause, non-fatal (recurrent) symptomatic VTE, or readmission for COPD exacerbation within 90 days after enrollment.

Confirmation of **(recurrent) symptomatic PE** requires symptoms of PE and a new or an extension of a previous intraluminal-filling defect in (sub)segmental or more proximal branches on PE-protocol chest CT pulmonary angiography.

Confirmation of **(recurrent) symptomatic DVT** requires symptoms of DVT and the following criteria: 1) In the absence of previous DVT investigations at baseline, a non-compressible venous segment on ultrasonography; 2) if there were previous DVT investigations at baseline, abnormal lower limb CCUS where compression had been normal; or, if previously non-compressible, a substantial increase (≥ 4 mm) in diameter of the thrombus during full compression.

Secondary efficacy end points include:

- Death from any cause within 90 days after enrollment.
- Nonfatal (recurrent) symptomatic VTE within 90 days after enrollment.
- Readmission for exacerbation of COPD within 90 days after enrollment.
- Length of hospital stay.

Safety

The primary safety end point is major bleeding within 90 days after enrollment.

Major bleeding is defined according to the guidelines of the International Society of Thrombosis and Haemostasis (20), as acute clinically overt bleeding associated with one or more among the following: a decrease in hemoglobin of 2 g/dL or more, a transfusion of two or more units of packed red blood cells, bleeding that occurs in at least one of the following critical sites (intracranial, intraspinal, intraocular, pericardial, intraarticular, intramuscular with compartment syndrome or retroperitoneal), bleeding that is fatal (defined as a bleeding event that the central independent committee adjudicate as the primary cause of death or contributing directly to death) and bleeding that necessitates surgical intervention.

Secondary safety end points include:

- Clinically relevant non-major bleeding within 90 days after enrollment.
- Serious adverse events (**SAE**) within 90 days after enrollment.

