4.3 Adjudication

A committee of two clinical experts from Ramon y Cajal Hospital (Spain) who will be unaware of the study-group assignments will confirm all outcomes and classify the cause of all deaths as due to PE, due to COPD, due to bleeding, or due to another cause.

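### Investigators manage intervention patients and are barred from managing controls, so a difference in the composite could be credited to the whole package of care but not to the PE search alone.

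*Protocol*

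**What the plan says.** Protocol 4.2 (Investigators) lists the investigators' duties, among them "obtaining informed consent, and management of patients randomized to the intervention". The next sentence is the restriction: "Participating investigators will not be allowed to manage patients randomized to usual care". Neither document says who treats the controls, beyond the Abbreviated Protocol, where they receive "standard clinical management of their exacerbations, as deemed appropriate by the attending physician".

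Protocol 2.5 describes background care: "All patients will receive standard clinical management (usual care) for their COPD exacerbation". It leaves the content of that care to clinician preference and local standards. After discharge, both arms are to follow the same national and international recommendations.

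The trial is "open-label with blind end-point evaluation" (Protocol 2.1). Protocol 2.7 defines the main efficacy outcome in three parts: "composite of death from any cause, non-fatal (recurrent) symptomatic VTE, or readmission for COPD exacerbation within 90 days after enrollment". Protocol 4.3 provides two experts "who will be unaware of the study-group assignments will confirm all outcomes". Randomization is central, concealed and stratified by center (Protocol 2.4), and SAP 3.5.2 adds center-stratified results for the primary end points.

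**The concern.** The hypothesis in Protocol 1.2 is about one thing: searching for PE with D-dimer and, if positive, CT. To read an outcome difference as the effect of that search, the rest of the care must be comparable between arms. Under 4.2, one set of physicians manages one arm and a different, undescribed set manages the other. Under 2.5, the COPD care they give is not standardized.

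Readmission for COPD is partly a clinical judgement, made without blinding, and it depends on how the exacerbation was treated and when the patient was discharged. If the two sets of clinicians differ in any of these, the composite can move although the search does nothing, or a real effect of the search can be hidden. A search for PE acts mainly through the minority found to have PE, whereas a difference between clinicians reaches the whole arm.

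**Working it through.** **Step 1. What *management* covers in 4.2.** The word has two uses in the documents. Protocol 2.4 and the deviation table in SAP 7 use it for the allocated strategy. The Abbreviated Protocol and Protocol 2.5 use it for clinical care of the exacerbation. In 4.2 the same verb is applied to controls, who have no protocol pathway to deliver. For them, managing can hardly mean anything but clinical care, so the natural reading of "management of patients randomized to the intervention" is also clinical care. The text does not exclude the narrower meaning.

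**Step 2. What the safeguards can remove.** Under the natural reading, clinician group and arm are fully collinear within each center.
- Stratifying or adjusting by center cannot separate two factors that coincide inside every center.
- Blinded adjudication (4.3) and blinded image reading (4.6) check whether an event meets its definition. They cannot undo a real difference in treatment, or in the decision to readmit.
- The e-CRF records exacerbation treatment (Protocol 3.3) and, at follow-up, concomitant medication and the cause of rehospitalization (3.4). Neither document plans to compare exacerbation treatment or concomitant medication by arm as a check on co-intervention. The treating service and the readmitting service are not listed entries.

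**Step 3. The plan's sample size.** Inputs (Protocol 2.10, SAP 2.2): 40% v 30%, 80% power, two-sided 5%.

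n = [1.960·√(2·0.35·0.65) + 0.842·√(0.40·0.60 + 0.30·0.70)]² / 0.10² = 356 per arm

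The unpooled form gives 353.2, so the stated 355 is reproduced. Power at 355 is 79.9%. No change in sample size follows from this point.

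**Step 4. What a difference in care would do.** The documents give no figure for a clinician effect, so shifts of 2, 3 and 4 points are assumptions. Take 355 per arm, a 40% control rate, no effect of the search, and an intervention rate of 40% minus d. With SE₀ the pooled and SE₁ the unpooled standard error, Φ the standard normal distribution function:

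P(significant) = Φ[(d − 1.960·SE₀)/SE₁] + Φ[(−d − 1.960·SE₀)/SE₁]

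| d (points) | SE₀ | SE₁ | Favoring intervention | Either direction |
|---|---|---|---|---|
| 0 | 0.0368 | 0.0368 | 2.5% | 5.0% |
| 2 | 0.0366 | 0.0366 | 7.9% | 8.5% |
| 3 | 0.0365 | 0.0365 | 12.7% | 13.0% |
| 4 | 0.0364 | 0.0364 | 19.4% | 19.5% |

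**Step 5. The opposite direction.** Suppose the search truly gives the planned 10 points and better care of controls offsets 2, 3 or 4 of them. The first term of the same formula, with net d of 8, 7 or 6 points, gives power of 60%, 49% or 38% instead of 79.9%.

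**Step 6. Scale.** Protocol 1.1 cites PE prevalences of 25%, 16% and 3.3%. Assume that the search works only through patients with PE and that they share the 40% event rate. Preventing every one of their events would then lower the composite by at most 0.25 × 40 = 10.0, 0.16 × 40 = 6.4 or 0.033 × 40 = 1.3 points. Against those ceilings, a few points from differences in care is not negligible.

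**The case against.** The strongest reply is that *management* in 4.2 means only the allocated strategy. Investigators would then run the D-dimer/CT pathway, and the ban would simply keep them from bringing a PE search into control care. The documents do not rule this out. If it is what was meant, one sentence settles the matter. The ban is a sensible guard against contamination on either reading, although neither document gives that reason.

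Several stronger conclusions that a reader might draw do not stand:
- *4.2 contradicts 2.5.* It does not. Section 2.5 describes the kind of care and 4.2 who gives it. Section 2.5 nowhere promises the same clinicians in both arms.
- *Care and follow-up do differ by arm.* The documents show only that care may differ. Scheduled visits are identical (Protocol 2.8, 3.4), post-discharge recommendations are common to both arms, and nothing says who decides a readmission up to 90 days later.
- *A difference could not be interpreted at all.* SAP 2.1 describes a comparison of two strategies of care, and concealed randomization keeps the comparison of the packages valid.

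It is also fair to say that any bias of 2 to 4 points, whatever its cause, would give the rejection rates shown. They illustrate sensitivity and are no evidence that such a bias exists.

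What remains is that, on the natural reading, clinician group and arm coincide, background care is discretionary, and no safeguard or planned analysis addresses it.

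**Conclusion.** The point holds in a limited form. As 4.2 is worded, the trial compares an active search delivered by investigators with usual care delivered by others. A difference in the composite could be attributed to that whole package, but not to the PE search alone. This rests on reading *management* as clinical care, which is the more natural reading but not the only one.

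The size and direction of any bias are unknown. For illustration only, assumed shifts of 2, 3 or 4 points favoring the intervention raise the chance of a significant result with no search effect from 5% to about 8.5%, 13% or 19.5%. Shifts the other way would mask a benefit. Readmission is the most exposed component. Death is less discretionary but still open to differences in care. The documents do not support saying that bias has occurred, or that the randomized comparison is invalid.

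**What to change.** **Protocol 4.2, reconciled with 2.5.** State that investigators' management covers only the allocated D-dimer/CT strategy and its PE consequences. Keep the ban on investigators managing controls. State that routine COPD care comes from the same attending services in both arms. This concerns who is responsible, not what treatment is given.

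**SAP, for all patients including those already enrolled.** Add a descriptive comparison by arm of exacerbation treatment, concomitant medication, length of stay and, where obtainable, the treating and readmitting service. For this purpose, length of stay needs a start date that every patient has: SAP 2.5.6 counts from diagnosis of PE, which patients without PE lack. Where the present rule was applied, describe the effect as that of the whole strategy as delivered.

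**Cost.** Amendment wording, a few lines in the SAP and, if the services are to be captured, a small e-CRF addition. Sites where investigators now give routine COPD care to intervention patients would have to hand it over, as they already must for controls. The wording change comes late: this protocol version is dated September 2018, and enrollment was expected from late 2014 in a trial of about four years. It would affect few patients, so the comparison by arm and the description of the effect do most of the work.

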4.3 Adjudication

A committee of two clinical experts from Ramon y Cajal Hospital (Spain) who will be unaware of the study-group assignments will confirm all outcomes and classify the cause of all deaths as due to PE, due to COPD, due to bleeding, or due to another cause.

4.4 Data Safety Monitoring Board

The DSMB will consist of independent clinicians and statisticians. At regular intervals the DSMB will review safety and outcome data provided by SH Medical and report to the Chairman of the Steering Committee. The DSMB will also conduct analyses of data at the request of the Steering Committee.

In order to assure patient safety, the DSMB will be provided in a timely fashion with data on safety end points in periodic cumulative reports.

4.5 Data management

Study data will be entered into the electronic case report forms (e-CRFs), embedded in the SLICE database by the authorized principal investigators or sub-/co-investigators (www.estudioslice.org). The data-management of the study database maintenance will be performed by the CRO (SH Medical) according to its own Standard Operating Procedures. Data evaluated by the DSMB will be extracted periodically from the trial database. After data base lock, the database will be transferred to the Chairman.

4.6 Central readings

Image interpretations for all radiological tests except venous ultrasonography will be based on agreement of two certified readers in the SLICE trial who were from Ramón y Cajal Hospital. Readers will be unaware of all clinical information and of the study arm.

5. CALENDAR

It is estimated that the trial duration will be 4 years. After legal approvals, it is expected that enrollment will begin the last trimester of 2014.

6. LEGAL ISSUES

The trial will be carried out:

- In compliance with the protocol.
- In compliance with Conventions of the Council of Europe on Human Rights and Biomedicine, UNESCO Declaration.
- In accordance with the Declaration of Helsinki, version as of Oct. 1996, the International Conference on Harmonization (**ICH**) Harmonized Tripartite Guideline for Good Clinical Practice (**GCP**) and in accordance with applicable Spanish regulatory requirements.

-Informed consent: Ethical and legal requirements in accordance with international declarations (e.g., Declaration of Helsinki, Conventions of the Council of Europe on Human Rights and Biomedicine, UNESCO Declaration) will be fulfilled in this study. The person who informs the subject should be a physician. An informed consent document that includes both information about the trial and the consent form will be prepared and given to the subject. This document will comply with all local requirements and the requirements set out in GCP. The document must be in a language understandable to the subject and must specify who informed the subject. After reading the informed consent document, the subject is asked to give consent in writing.

The subject's consent must be confirmed at the time of consent by the personally dated signature of the subject or the subject's legally authorized representative (means an individual or judicial or other body authorized under applicable law to consent on behalf of a prospective subject to the subject's participation in the procedures involved in research). A copy of the signed consent document must be given to the subject or the subject's legally authorized representative. The original signed consent document will be retained by the investigator (a copy may be requested by the sponsor).

The subject must be informed that his/her medical records may be examined by Clinical Quality Assurance auditors appointed by the Sponsor, or by appropriate IEC/IRB members or by inspectors from regulatory authorities. Should a protocol amendment be made, the subject consent form and subject information form may need to be revised to reflect the changes to the protocol. It is the responsibility of the investigator to ensure that an amended consent form is reviewed and received approval/favorable opinion from the ICE or IRB, and that it is signed by all subjects subsequently entered in the trial and those currently in the trial, if affected by the amendment.

-Confidentiality: Individual subjects medical information obtained as a result of this study is considered confidential (according to Spanish regulations, LOPD 15/1999) and disclosure to third parties is prohibited with the exceptions noted below. Subject confidentiality will be further ensured by utilizing subject identification code numbers to correspond to treatment data in the computer files. Such medical information may be given to the patient's personal physician or to other appropriate medical personnel responsible for the subject's welfare. Data generated as a result of this trial are to be available for inspection on request by the participating physicians, the Sponsor's representatives, by the IEC/IRB and the regulatory health authorities.

-Insurance cover: The Sponsor will take out no-fault insurance cover for all subjects included in the trial. The conditions of this insurance cover are available to the investigators on request. The investigator can make this information available to subjects on request.

-Adverse events: Following the subject's written consent to participate in the study, which must be obtained before any screening procedures, all SAEs must be collected, including those thought to be associated with clinical study

procedures. All SAEs must be reported to the Sponsor (Hospital Ramón y Cajal) within 24 hours of awareness.

-Publication policy: The Sponsor is dedicated to supporting the process of free exchange of relevant scientific information. Any publication of the results of this trial must be consistent with the publication policy of the Sponsor (Hospital Ramón y Cajal) and Executive Committee. Some general rules are laid down below.

This study represents a joint effort between the Sponsor and the investigators. A publication policy will be presented by the Writing Committee and approved by the Steering Committee:

- All investigators and members of these committees agree to abide by the policy.
- Agreement on authorship of the main paper -Conditions for secondary manuscripts.
- It is foreseen that the Study Chairman, Co-chairman and the Writing Committee will prepare a manuscript plan to ensure timely and high-quality presentation and publication of the study results and provide this to the Sponsor for due consideration. Local publication of part(s) of the results is not allowed before the publication of the main study.
- The Study Chairman and Co-chairman will submit any manuscript to members of the Steering Committee for comment and release prior to the actual submission to a learned society or scientific journal.
- After this, Investigators may submit secondary papers, but these should be provided according to the publication policy for review and approval.

One week should be allowed for review by the Sponsor of abstracts planned to be submitted to a learned society, and 3 weeks should be allowed for review of papers planned to be submitted to a scientific journal.

